### 3.4 Re-registration Eligibility Criteria (For patients who crossover from arm 1 nivolumab alone to dual agent nivolumab and ipilimumab upon progression)

#### 3.4.1 Disease Status

- Measurable disease as defined in [Section 11.0](#).
- Locally advanced/unresectable or metastatic disease.
- Patient MUST have had progressive disease (radiographic or clinical) while on arm 1 single agent nivolumab while registered to A091401.

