#### 4.6 Re-Registration (Step 2) at the time of progression

Upon confirmation of progression, patients who were initially assigned to nivolumab alone (Arm 1) will be allowed to cross over to the dual agent arm (Arm 2).

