## 7.2 Crossover to Dual Agent Nivolumab and Ipilimumab upon Progression on Arm 1 (single agent nivolumab)

Upon documentation of progression on arm 1 and confirmation of eligibility criteria as per [Section 3.4](#), patients may be re-registered and initiate dual-agent therapy. All parameters outlined in [section 7.0](#) are applicable. NOTE: Treatment beyond progression in the first 12 weeks, as per [section 7.1](#), is applicable to patients receiving crossover dual agent therapy.

Administer nivolumab prior to ipilimumab (follow institutional standard for timing between agents) as specified below:

Agent	Dose & Route	Frequency	Cycle Length (ReRx)
nivolumab	3mg/kg IV over 30 minutes	Every 3 weeks	42 days
ipilimumab	1mg/kg IV over 90 minutes	Every 3 weeks	42 days

\*\*The above regimen will be followed for 4 doses, followed by:

Agent	Dose & Route	Frequency	Cycle Length (ReRx)
nivolumab	3mg/kg IV over 30 minutes	Every 2 weeks	42 days

Though treatment is every 2 or 3 weeks, **a cycle will consist of 6 weeks in length** and therapy can be continued until patient develops progressive disease or unacceptable toxicity or withdraws from treatment. In the absence of these 3 events, treatment will continue for a maximum of 108 weeks (i.e. 18 cycles) including the single agent nivolumab received prior to crossover to dual agent therapy.

To determine response via RECIST v1.1, patients will undergo radiographic imaging every 8 weeks while on study treatment.

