#### 11.4.4 Overall Objective Status

**Important: Refer to [Section 11.1](#) for a full description of the correct baseline scan to use due to the retreatment after PD during treatment in the 1st 12 weeks, as well as baseline scan to be used for crossover treatment.**

The overall objective status for an evaluation is determined by combining the patient's status on target lesions, target lymph nodes, non-target lesions, non-target lymph nodes, and new disease as defined in the following table:

Target Lesions & Target Lymph Nodes	Non-Target Lesions & Non-Target Lymph Nodes	New Sites of Disease	Overall Objective Status
CR	CR	No	CR
CR	Non-CR/Non-PD	No	PR
PR	CR Non-CR/Non-PD	No	PR
CR/PR	Not All Evaluated*	No	PR
SD	CR Non-CR/Non-PD Not All Evaluated*	No	SD
Not all Evaluated	CR Non-CR/Non-PD Not All Evaluated*	No	Not Evaluated (NE)
PD	Unequivocal PD CR Non-CR/Non-PD Not All Evaluated*	Yes or No	PD
CR/PR/SD/PD/Not all Evaluated	Unequivocal PD	Yes or No	PD
CR/PR/SD/PD/Not all Evaluated	CR Non-CR/Non-PD Not All Evaluated*	Yes	PD

\* See [Section 11.4.3.1](#)

**11.4.5 Symptomatic Deterioration:** Patients with global deterioration of health status requiring discontinuation of treatment without objective evidence of disease progression at that time, and not either related to study treatment or other medical conditions, should be reported as PD due to “symptomatic deterioration.” Every effort should be made to document the objective progression even after discontinuation of treatment due to symptomatic deterioration.

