### 12.2 Crossover

Any patient that is originally randomized to the Nivolumab alone arm (Arm 1) will have the option to cross over to the nivolumab + ipilimumab combination therapy **ONLY IF** they were removed due to disease progression. Eligibility must be evaluated as per [Section 3.4](#) and patients must be re-registered to the crossover portion of the study per [Section 4.6](#).

Once patients re-register and cross-over to the nivolumab + ipilimumab dual therapy, all cross over patients must have a scan  $\leq$  28 days of starting their new treatment as per [Section 5.0](#).

Crossover patients previously removed from Arm 1 for progression who were being followed for survival will no longer be followed by the survival schedule nor survival case report form but will proceed to the crossover treatment schedule, crossover test schedule, and crossover case report forms. Cycles/data collection will resume from the last treatment cycle patient received. Contact the data manager for assistance with RAVE data entry.

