## 13.4 Secondary Endpoints

- Evaluating adverse event rates (NCI CTCAE v4.0), within each study treatment arm. Categorical data analysis will be used to summarize adverse event rates and as a maximum severity during treatment for each patient and AE classification.
- Evaluating duration of response, clinical benefit rate (CBR), progression-free survival (PFS), and overall survival (OS), within each study treatment arm. Patients having PD within the first 12 weeks of starting treatment which is not a PD at their 4 week confirmation assessment will not be classified as having PD for time to event analyses. That is, estimates for response, CBR, and PD endpoints will not be censored at the first PD in such cases. Patients who are unable to continue treatment for a 4-week confirmation of PD occurring within the first 12 weeks of treatment will be counted as having PD at their first date of PD during the treatment period (eg, initial, crossover). In addition, disease assessment data beyond the date of crossover will not be included in the evaluation of the primary endpoint and for those patients crossing to dual agent treatment from single agent treatment. Such patients will be censored for estimating

duration of response, CBR, and PFS. Patients will be additionally censored at their most recent disease assessment prior to receiving any anti-cancer therapy after ending study treatment.

Kaplan-Meier methodology will be used to evaluate time to event endpoints: duration of response (time from first response to disease progression), PFS (time from randomization to the earliest of either disease progression or death from any cause), and OS (time from randomization to death from any cause). The CBR will be evaluated by counting up the number of patients with a response or stable disease (PR, CR, SD) and dividing by the total number of evaluable patients. Cumulative Incidence Function methodology may be used, as appropriate.

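### Section 13.4 says crossover patients are censored for PFS, DoR and CBR, yet crossover requires a progression that is already the PFS and DoR event; the sentence should be replaced

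*Combined protocol and SAP*

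**What the plan says.** Section 13.4 defines "PFS (time from randomization to the earliest of either disease progression or death from any cause", and DoR as the time from first response to progression. CBR is a count of patients with response or stable disease, obtained by "dividing by the total number of evaluable patients". The same section excludes disease assessments after crossover from the primary endpoint. It then adds, of patients who cross from single to dual agent, "Such patients will be censored for estimating" DoR, CBR and PFS. No censoring date follows, and nothing is said about a progression already on record.

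The crossover rules are consistent on one point: progression comes first.

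- Section 3.4.1: "Patient MUST have had progressive disease (radiographic or clinical) while on arm 1 single agent nivolumab".
- Section 3.4.2: patients taken off Arm 1 for any other reason cannot re-register.
- Section 4.6: "Upon confirmation of progression, patients who were initially assigned to nivolumab alone (Arm 1) will be allowed to cross over".
- Section 7.2: "Upon documentation of progression on arm 1 and confirmation of eligibility criteria".
- Section 12.2: crossover is open only if "they were removed due to disease progression".

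Clinical progression is not a loophole. Under Section 11.4.5, global deterioration without objective progression "should be reported as PD due to" symptomatic deterioration.

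**The concern.** A patient reaches crossover only by having progressed on Arm 1. Under the plan's own definitions that progression is the PFS event and, in a responder, the DoR event. So there is no evident group for whom censoring at crossover is needed for PFS or DoR. The sentence either does nothing or removes events. If it removes them, the censoring is informative, because it falls exactly on patients who have just progressed. For CBR the instruction has no defined meaning, since a proportion has no time axis.

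Two competent programmers could therefore report different Arm 1 PFS and DoR from the same data. The next sentence of Section 13.4 strengthens the literal reading. It says patients are additionally censored before other anti-cancer therapy and does give a date, which makes crossover look like a working censoring rule too. The within-arm biomarker analyses of PFS in Section 13.5 would inherit the ambiguity. Section 13.5 also restarts the clock at crossover treatment, so a literal application would leave the Arm 1 progression uncounted in both the initial and the crossover analysis.

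**Working it through.** The plan states no PFS, DoR or CBR figure, so there is nothing to reproduce. The check asks what each reading does to a Kaplan-Meier estimate of six-month PFS on Arm 1.

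**Inputs from the documents.** Section 1.1 gives historical six-month PFS in previously treated patients of 14% (active regimens) and 8% (inactive regimens). Scans are every 6 weeks for 12 weeks, then every 8 weeks (Section 5.0), so at weeks 6, 12, 20 and 28. Crossover needs at least 10 weeks of nivolumab (Section 3.4.2), so progressions seen at week 12 or later can be affected. Arm sizes are 38, 12 and 24 evaluable patients (Section 13.3).

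**Assumptions.** PFS is exponential. A share c of progressions seen from week 12 on is followed by crossover. The documents give no value for c; 20%, 40% and 60% are used.

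**Step 1: true curve.** With six months taken as 26.09 weeks, the weekly hazard is −ln(0.14)/26.09. This gives S(6) = 0.636, S(12) = 0.405 and S(20) = 0.222.

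**Step 2: events kept (data cut).** The last scan before six months is week 20, so the curve reads S(20) = 22.2% whatever the value of c. The gap from 14% comes from scan timing and has nothing to do with crossover. The comparison base is therefore 22.2%, not 14%.

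**Step 3: events replaced by censoring at the progression date.**

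- After week 12: K12 = S(6) − (1 − c)(S(6) − S(12)).
- At six months: K12 × [1 − (1 − c)(S(12) − S(20))/S(12)].

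For c = 0.2: K12 = 0.636 − 0.8 × 0.231 = 0.451. The bracket is 1 − 0.8 × 0.183/0.405 = 0.638. The product is 0.288.

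The 8% input uses S(6) = 0.559, S(12) = 0.313 and S(20) = 0.144.

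| Assumed share censored | 14% input | 8% input |
|---|---|---|
| Events kept | 22.2% | 14.4% |
| 20% | 28.8% | 20.6% |
| 40% | 36.2% | 27.8% |
| 60% | 44.5% | 36.1% |

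A simulation of 300,000 patients at the 14% input gave 28.7%, 36.1% and 44.4%.

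**Step 4: events lost by week 20** = n × (S(6) − S(20)) × c, with the 14% input, where S(6) − S(20) = 0.636 − 0.222 = 0.414. For c = 20/40/60% this is about 3.2/6.3/9.5 of 38, 2/4/6 of 24, and 1/2/3 of 12.

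**Step 5: separate check.** A different model ignores scan timing and thins the hazard after week 10. It moves a 10% six-month PFS (also quoted in Section 1.1) to 14%, 20%, 29% and 41% for shares of 25%, 50%, 75% and 100%. A simulation with 38 patients and scheduled scans moves in the same direction, and with events kept the estimate does not change with the share.

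DoR was not quantified. It is affected only in responders who progress and cross over, and the documents give no basis for that number.

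**The case against.** The strongest reply is that the plan uses 'censored' to mean a data cut. Earlier in the same bullet, Section 13.4 says that response, CBR and progression estimates are not censored at an unconfirmed early progression. Section 13.3 applies the word to the binary primary endpoint. For a proportion it can only mean that later assessments stop counting. The disputed sentence lists CBR and follows directly on a data-exclusion sentence. This stands, and it makes the data cut the better-supported reading. It does not remove the conflict. The preceding exclusion names only the primary endpoint, and for PFS and DoR, which are Kaplan-Meier endpoints, 'censored' has a standard technical meaning.

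A reader might also infer that patients are censored at a later crossover date, so that time after progression counts as progression-free, since Section 3.4.2 allows re-registration up to 12 months after the last dose. The documents do not support that. No text says to discard a recorded progression, and the definition takes the earliest of progression or death. Likewise, a reader might infer that crossover patients leave the CBR denominator, but Section 13.4 fixes it as all evaluable patients.

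One further objection stands. A progression in the first 12 weeks that is not confirmed at the 4-week scan is not classed as progression, and the first date is used for patients unable to continue to that scan. A patient who progresses at week 12 and crosses over without the repeat scan is not squarely covered. In the illustration these week-12 cases are 0.231/0.414, or about 56%, of the affected events by week 20.

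**Conclusion.** The conflict is real. The censoring sentence contradicts the PFS and DoR definitions beside it and has no meaning for CBR. Read as a cut of post-crossover data, which the plan's own usage favours, it leaves PFS and DoR unbiased. Applied literally, it biases Arm 1 PFS upward, and DoR in responders who later cross over. In the illustration, six-month PFS rises by 6.6 to 22.3 percentage points with the 14% input (28.8 − 22.2 and 44.5 − 22.2). All such figures rest on assumed crossover shares, exponential PFS and historical rates from other regimens; they show direction and possible scale and do not predict this trial's result.

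It would go too far to infer that the analysis will be wrong, or that the trial's conclusions are at risk. The documents do not show which reading was intended. Only Arm 1 secondary endpoints are exposed. The primary endpoint has its own crossover exclusion in Section 13.3, no between-arm comparison is planned, and OS, the decision rules and the sample sizes are untouched.

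**What to change.** Replace the censoring sentence in Section 13.4 with:

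*The PD on Arm 1 that led to crossover is the PFS/DoR event on its own date, including PD in the first 12 weeks when the patient crosses over without a 4-week repeat scan; disease assessments after crossover are excluded from the initial-treatment analyses; no patient is censored for crossing over; crossover patients stay in the CBR denominator and are classified by best status before crossover.*

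The clause on the first 12 weeks settles a case the current text leaves open. It is a substantive analysis choice, so the study team should confirm it as such.

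The cost is one sentence. It needs no new data and changes no decision rule. If the data cut was always intended, PFS and DoR results do not change, apart from any early-progression cases that the new clause settles. If the literal reading was intended, reported Arm 1 PFS and DoR will be lower.

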- \*\*\* Patients who do not progress on treatment (i.e. removal for toxicity or withdrawal of consent) are followed every 6 months for both survival and disease status for at least three years post-randomization or until death, whichever comes first. Upon progressive disease (at any time), survival information is required every 6 months for 3 years. See also [Section 12](#).
- \*\*\*\* Drug dosages need not be changed unless the calculated dose changes by  $\geq 10\%$ .
- † Oxygen saturation should be assessed at rest and after 1 minute walk.
- $\pi$  Solicited AEs are to be collected starting at baseline until off treatment (See [Section 9.1](#)). Routine AEs are to be collected starting after registration. See [Section 9.3](#) for expedited reporting of SAEs.
- $\Psi$  Albumin, alkaline phosphatase, total bilirubin, bicarbonate, BUN, calcium, chloride, creatinine, glucose, potassium, total protein, SGOT[AST], SGPT[ALT], sodium.
  - 1 To be completed after pre-registration and prior to registration ( $\leq 21$  days prior to treatment), see [Section 1.9](#) and [Appendix I](#). NOT required for re-registration.
  - 2 Labs may be performed +/- 3 days from date required.
  - 3 For women of childbearing potential (see [Section 3.2](#)). Must be done  $\leq 7$  days prior to registration. Also, must be done  $\leq 7$  days prior to re-registration.
  - 4 See [Section 6.2](#). Central pathology review is only required for registration, not required for re-registration.
  - 5 Baseline scans can include either: 1) a CT, spiral CT, or MRI, or 2) an FDG-PET scan and diagnostic CT performed with both IV and oral contrast, and the CT acquired with 5 mm or less slice thickness. Supporting documentation is to be submitted, per [Section 6.1.1](#).
- A Every 6 to 8 weeks.
- B Perform every 4 weeks x 4 in arm 1 (nivolumab alone). Perform every 3 weeks x 4, then every 2 weeks x 1 in arm 2 and crossover to dual agent therapy (nivolumab + ipilimumab).

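### Duration of response has no rule for a responder who dies without recorded progression, and the censoring this implies overstates duration

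*Combined protocol and SAP*

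**What the plan says.** Section 13.4 (Secondary Endpoints) states that "Kaplan-Meier methodology will be used to evaluate time to event endpoints" and then defines three of them in one sentence:

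- the response endpoint stops at progression alone: "duration of response (time from first response to disease progression");
- the second endpoint also stops at death: "PFS (time from randomization to the earliest of either disease progression or death from any cause");
- the third is OS, from randomization to death from any cause.

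Two censoring rules reach duration of response. For patients who cross over, "Such patients will be censored for estimating" duration of response, clinical benefit rate and PFS. In addition, "Patients will be additionally censored at their most recent disease assessment prior to receiving any anti-cancer therapy after ending study treatment". Neither rule mentions death. The paragraph closes with "Cumulative Incidence Function methodology may be used, as appropriate", without naming an endpoint or a competing event.

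Two other places matter. Section 11.4.5 has "Patients with global deterioration of health status requiring discontinuation of treatment without objective evidence of disease progression at that time" reported as progression, provided the decline is not related to study treatment or other medical conditions. The Study Calendar (Section 5.0) says that patients who stop treatment without progressing "are followed every 6 months for both survival and disease status".

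**The concern.** Death is named as an event for PFS and OS and left out for duration of response, all in one sentence. If a responder dies without recorded progression, the plan supplies no event. Kaplan-Meier then has nothing to do with that patient but censor, which treats the response as continuing with the same future risk of progression as in the responders who are still alive.

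The protocol itself foresees such deaths. Section 13.7 has a suspension rule for grade 5 events other than progressive disease. Section 9.4.2 warns of fatal immune-mediated events with ipilimumab. Section 1.5 reports three deaths linked to pulmonary toxicity with nivolumab. A fatal toxicity in a responder would drop out of the event count, so a harm of treatment would read as a sustained response.

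Section 13.1 repeats every endpoint in each histologic cohort, and Section 13.5 evaluates duration of response again after crossover, so the definition is used many times.

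**Working it through.** The plan gives no assumed duration of response, event count or share of deaths without progression, so there is no figure of its own to reproduce.

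**Step 1: direction.** Take the censoring date to be the date of death. The number at risk at every time is then the same whether death is censored or counted. Counting a death at a time when n responders are at risk multiplies the curve by (1 − 1/n); censoring it leaves that factor out. From that time on, the progression-only curve therefore lies above the curve that counts death, until both reach zero. If no responder dies without recorded progression, the two curves are identical.

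**Step 2: which deaths are affected.** Deaths preceded by a recorded progression are not affected, including progression recorded as symptomatic deterioration under Section 11.4.5. Deaths after new anti-cancer therapy are already censored by the stated rule. What remains is mainly toxicity deaths, which Section 11.4.5 excludes by its wording, intercurrent deaths, and sudden deaths between assessments.

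**Step 3: size under assumptions.** Assume constant hazards and a progression-only median of 12 months, so λ = ln 2 / 12. Let the hazard of death without progression be kλ. Then:

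- share of first events that are deaths: k / (1 + k);
- median with death counted: 12 / (1 + k);
- proportion still in response at 12 months: 0.5^(1 + k).

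| k | Death share of first events | Median with death counted (months) | In response at 12 months |
|---|---|---|---|
| 0 | 0% | 12 | 50% |
| 0.05 | 0.05/1.05 = 4.8% | 12/1.05 = 11.4 | 48% |
| 0.10 | 0.10/1.10 = 9.1% | 12/1.10 = 10.9 | 47% |
| 0.25 | 0.25/1.25 = 20% | 12/1.25 = 9.6 | 42% |

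The progression-only Kaplan-Meier estimate targets 12 months and 50% in every row. Both the 12-month median and the death shares are assumptions.

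**Step 4: weight of one death.** Expected responders per arm at the design alternatives (Sections 13.3.1 to 13.3.3):

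- initial cohort: 38 × 20% = 7.6, so one death is 1/7.6 = 13%;
- GIST: 24 × 20% = 4.8, so 1/4.8 = 21%;
- LPS and UPS/MFH: 12 × 25% = 3.0, so 1/3.0 = 33%.

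An illustration with eight responders and invented end times of 2, 4, 5, 6, 8, 10, 13 and 18 months: the median is 6 months if all eight are events. It is 8 if the month-4 end is a death and is censored, and 10 if the month-4 and month-6 ends are both censored deaths.

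**Step 5: would cumulative incidence repair it?** Use the last row of the table. The cumulative incidence of progression at 12 months is 0.80 × (1 − 0.42) = 0.46, so its complement is 0.54. That compares with 0.50 by progression-only Kaplan-Meier and 0.42 with death counted. The complement still counts patients who died without progressing as not progressed, so it does not end a response at death.

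**The case against.** The strongest reply has four parts.

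First, a reader might infer that the plan instructs analysts to count dead responders as still responding. It does not say so. The plan is silent, and censoring at death is only what its event and estimator imply. That stands as a limit on the wording, but no other handling is offered.

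Second, among the three endpoints in that sentence, duration of response is the only one for which death can compete. The cumulative incidence sentence may therefore show that the authors saw the issue. It could equally refer to time to progression, a secondary objective in Section 2.2.2. It is optional, names neither an endpoint nor a competing event, and estimates a different quantity (step 5).

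Third, a reader might infer that disease-related deaths in general are lost. Section 11.4.5, together with scans every 6 and then 8 weeks, means that many would carry a progression date. This narrows the gap but leaves toxicity, intercurrent and sudden deaths.

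Fourth, the effect may be small against sampling error. With 8 responders and a true 12-month proportion of 50%, the standard error is about √(0.25/8) = 0.18, well above the shift of 0.02 to 0.08 in step 3. That is fair. However, a small number of responders does not cancel an upward bias, and it makes one censored death more visible.

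**Conclusion.** The point holds as a gap in one secondary definition. Following Section 13.4 as written overstates duration of response whenever a responder dies without recorded progression. The size cannot be derived from the documents. On an assumed 12-month progression-only median, the median with death counted would be 11.4, 10.9 or 9.6 months for assumed death shares of about 5%, 9% or 20%. With no such death there is no difference.

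Two stronger readings are tempting. One is that arms will have only 2 to 5 responders, so that one death is 20% to 50% of them. The counts of 2, 3 and 5 in Section 13.3 are minimum counts for declaring activity. At the alternatives the expected numbers are 3.0, 4.8 and 7.6, and one death is about 13% to 33%. The other is that the trial's conclusions are at risk. The primary endpoint, sample sizes and decision rules rest on confirmed response, the arms are not compared, and OS, reported alongside, counts death as its event. What is affected is a descriptive endpoint, though one that may inform larger studies. The change is worth making before analysis.

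**What to change.** In Section 13.4, define duration of response as the time from first documented response to the earlier of disease progression or death from any cause, with the same censoring rules as PFS. Use the same end events in the crossover analysis of Section 13.5.

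If the sponsor prefers to keep progression as the only event, the endpoint should be labelled time to progression among responders, with death prespecified as a competing event. That is a legitimate but different quantity.

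The cost is one clause. Deaths are already collected for PFS and OS, so no new data are needed. The reported duration may be slightly shorter.
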